Maximal Oxygen Consumption (VO_{2max}). Aerobic fitness will be determined by measuring maximal O₂ consumption (VO_{2max}) during a stationary bicycle exercise test. Provider monitoring will follow The American College of Sports Medicine's (ACSM) Guidelines for Exercise Testing and Prescription and AdventHealth TRI BATS-Pilot SSP. Heart rate, blood pressure and ECG will be recorded throughout this test. During the test, participants will breathe through a low resistance mouthpiece and wear a nose clip. Expired gases will be measured by indirect calorimetry. Following a standardized warm up, participants will begin exercising at a moderate intensity with the workload (resistance on a cycle ergometer) increased every minute until the participant can no longer continue. VO₂ max tests will take as little time as possible in order to ensure that test termination is due to the participant reaching VO₂ max rather than terminating the test due to muscle exhaustion. A leveling-off (plateau) or decline in oxygen uptake should be demonstrated in order to be reasonably sure that a participant has achieved the maximum capacity for aerobic metabolism. However, there are several additional criteria that will be used to determine if maximal aerobic capacity is achieved. These criteria are: the respiratory exchange ratio (RER) increased to 1.10 or higher and the participant's heart rate increased to within 10 beats of the age-predicted maximum (208 – [0.7 x age]). This test will be supervised by a qualified Medical Provider as stated in AdventHealth TRI SOP 030.100.015 Procedural Staffing.

In the event of a positive stress test, participants are referred to their primary care physician. If the electrocardiogram (ECG) is determined to be a false negative, participant may be allowed to continue participating in the study.

Triaxial Activity Monitor: Two tri-axial accelerometer-based activity monitors will be placed during Visit 2. One will be placed on the wrist and the other on the triceps of the same arm. The monitors integrate motion sensor data from the tri-axial accelerometer to estimate the energy cost of free-living activity. The participant will wear the monitors for 5-7 days, except while showering or bathing. The participant will have the monitors removed and the data uploaded at Visit 2 or Visit 3.

Visit 2

Approximate visit time: ~ 3 hour

Review of Adverse Events, Concomitant Medications

Vital Signs

Body Weight (metabolic)

Collection of Activity Monitors

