- Participant reports >3 on P/D scale with explanation that the pain persists after the cessation of movement or if the participant reports >3 in any area besides the knee, upper or lower leg.
- Participant reports >18 on RPE scale.

Covid Testing: Participant must have a negative covid test prior to the next visit. Covid testing may take place on a separate visit when V2 is not within 1 week of V3.

Visit 3 Day -7

Approximate visit time: 10 minutes + Evening admission (~6:00pm) overnight.

Review of Adverse Events, Concomitant Medications

Body Weight

Fasting Finger Stick to collect glucose for clamp preparation. Participants will be asked to fast overnight prior to blood draw.

Standardized Meal: Participants will visit the metabolic kitchen at AdventHealth TRI on the evening before the glucose clamp and consume a standardized meal (10 kcal/kg) consisting of 50% carbohydrate, 15% protein, and 35% fat.

Visit 3 Day -6

Afternoon discharge (~2:00pm)

Vital Signs

Body Weight

Resting Metabolic Rate/Respiratory Quotient (RMR/RQ): Indirect calorimetry will be used at two times during the hyperinsulinemic-euglycemic clamp to measure the resting metabolic rate/respiratory quotient (RMR/RQ) and substrate utilization using a MAX II Metabolic cart (AEI Technologies, Pittsburgh, PA). The analyzer will be calibrated before each subject with standardized gases containing 5% CO₂, 21% O₂ and balance N₂. Subjects will be instructed to lie in a Semi-Fowler's position and remain motionless and awake during these periods. A transparent plastic hood connected to the device will be placed over the head of the subject. Calculations of O₂ consumption (VO₂) and CO₂ production (VCO₂) will be made by comparing a single measure of the O₂ and CO₂ concentrations of the testing room to continuous measurements of O₂ and CO₂ concentrations in expired air diluted in a constant air flow (20-50 L/min) generated by a pump. From the above, energy expenditure standardized for temperature, pressure, and moisture will be calculated at one-minute intervals.

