Insulin sensitivity (S_I) will be calculated using the formula: S_I = R_d / (steady state insulin level - basal insulin level) where steady state insulin equals the average insulin

concentration during the last 40 minutes of the clamp and basal insulin equals the average insulin level in the 30 minutes before starting the insulin infusion.

Fasting and insulin-suppressed FFA [IS-FFA] will be measured with an ultrasensitive FFA assay from Wako. Glucose disposal rate [GDR] will be expressed as mg/kg FFM [DEXA]/minute.

Metabolic flexibility of substrate oxidation

Before and during the steady state of the clamp, we will measure substrate oxidation using a MAX I Metabolic Cart (AEI Technologies, Pittsburgh, PA) to measure 'metabolic flexibility' as described by Kelley and Mandarino (19).

PHASE II – EXERCISE TRAINING INTERVENTION

Older sedentary participants will undergo 8 weeks of exercise training. Exercise training visits may extend up to 3 weeks through Phase III in rare circumstances to help accommodate staffing scheduling availability. The exercise program will be supervised by a certified exercise physiologist and will take place at the AdventHealth TRI exercise training facility. After the first week of exercise training at TRI, exercise training may take place remotely in rare circumstances, for example, if the participant has a short trip planned or the participant becomes ill and must skip a session during their intervention phase. Remote exercise will be brisk walking outside for a duration and intensity that is intended to be similar to the exercise performed at TRI. For remote exercise, the participant will be given and taught how to appropriately use a portable heart rate monitor to record their exercise sessions and a tracking log to document their session. A certified exercise physiologist will call a remotely exercising participant each day a remote exercise session is scheduled to provide instruction and to assess exercise compliance. Upon return to TRI, the data will be downloaded and added to the participant's exercise session files for analysis.

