Exercise compliance will be monitored for exercise training 4 days per week (minimum of 32 total sessions). Aerobic training will be 30 minutes of brisk walking, jogging, cycle ergometry. Walking will be the primary mode of aerobic exercise given its widespread popularity and ease of administration across a broad segment of the older adult population. Walking will be at a moderate intensity and determined based on Heart Rate (50-70% of Maximal HR from most recent VO₂max) and rating of perceived exertion using Borg's scale (ranges from 6 to 20). Other forms of endurance activity (e.g., stationary cycling) will be utilized on a limited basis when regular walking is contraindicated either medically or behaviorally. This is the exercise regimen that has demonstrated substantial increases in muscle size and strength in elderly people. See "Appendix: Schedule of Activities" for a table description of the procedures that will be performed during PHASE II.

PHASE III – POST-INTERVENTION TESTING

Following the exercise training intervention, participants in the OS group will participate in post-intervention testing. The testing procedures are a subset of those performed during the pre-intervention testing period (PHASE I). A detailed description of the procedures can be found above. The testing procedures will be taken over a 2-week period following the exercise intervention. See "Appendix: Schedule of Activities" for a table description of the procedures that will be performed during PHASE III.

Study Duration

Estimated start date for enrollment is Sept 30, 2019. Active recruitment and testing will continue until the end of the funding period or until 15 participants per group have been recruited. The study is funded by the National Institute of Aging until 01/31/2024.

Materials of Human Origin: Collection, Preparation, Handling and Shipping

Materials of human origin will be collected in the manner described in the specific study visits section of this protocol.

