Biospecimen samples will be stored in ultralow temperature freezers and liquid nitrogen dewars or other storage units located at the AdventHealth TRI Laboratory Room 2404. The AdventHealth TRI facility is secured via key card and equipped with a back-up generator system. Laboratory personnel in the facility have 24/7 key-controlled access to the laboratory. Chain of custody of biospecimen samples is maintained through requisition forms and in the StarLIMS database. Specimen tubes are coded, and specimen requests and distribution are documented.

The plasma/serum samples will be stored indefinitely, or until a sample is fully used. All biological specimens will be stored without identifiers or linkage codes.

After study aims have been achieved and study related endpoints have been measured and analyzed, any remaining biospecimens will be stored at the AdventHealth TRI Laboratory Room 2404 and will then be considered as “archived biospecimens.” Archived biospecimens will be used for any additional hypothesis-related experimentation or testing for the **purposes of this study, consistent with the original aims**, which cannot be predicted at the time the protocol is developed due to the evolving nature of scientific exploration.

Additionally, archived biospecimen samples may be stored indefinitely for future research. Archived biospecimens could be used for **separate research** by **both** AdventHealth Orlando scientists and scientists outside of AdventHealth TRI. This would be allowed for **research of any type** (without limitation to disease, process, or research methods) if it has scientific merit as determined by the Principal Investigator, with an additional review by the respective Program Director. For research outside of AdventHealth Orlando, a Material Transfer Agreement will be obtained, which will govern the transfer and chain of custody of the biospecimens outside of AdventHealth Orlando.

Study Outcome Measures (Endpoints)

The major outcomes of the study are collection of imaging of BAT by magnetic resonance imaging and circulating lipokines (12,13-diHOME) from 15 participants in each of the older athlete and sedentary groups. In addition, collection of all phenotype data are considered secondary outcome measures, including: Aerobic fitness (VO₂max test, DEXA, Muscle power and strength, Physical function (SPPB), and accelerometry data).

Data Management and Quality Plan

Data De-identification

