The primary purpose of this protocol is to understand the role of physical activity on BAT mass and circulating batokines, and how these variables relate to cardiac and physical function in older adults. A formal sample size calculation was not performed. Rather, we referred to published studies with similar experimental designs (determination of BAT mass by PET scan) as a guide for sample size determination. From the published literature we determine that an n=15 per group (active and sedentary) will provide sufficient statistical power to detect differences in BAT mass.

Statistical Analysis Plan

The analysis will involve multiple steps and draw on statistical methods ranging from simple descriptive statistics to the modeling of repeated measures outcome data accounting for potential missing observations. The major outcomes of the study, the BAT mass, circulating batokines, muscle mass, strength, power and quality, and VO₂max will be compared using an unpaired student t-test to explore baseline differences between older athletes and older sedentary groups. Additionally, repeated measures ANOVA will be performed on the dependent variables as a function of the exercise intervention in the older sedentary group. Multiple linear regression will be used to determine how BAT mass and circulating batokines explain variation in physical characteristics of muscle (strength, quality) and cardiovascular health (VO₂max). Sex will be explored as a biological variable.

Potential Risks and Benefits

Potential Benefits

Participants will likely receive no direct benefit from taking part in this research study.

Potential Risks

RMR/RQ. There is no physical risk associated with RMR/RQ. Other risks include a feeling of claustrophobia experienced by some participants while under the transparent “hood”.

Protection Against Risk:

- A member of the study staff will remain with the subject at all times to ensure his/her comfort.

Blood draws and Intravenous lines (lab samples and infusions, e.g.). There is a risk of pain, vasovagal syncope, hematomas, and/or infection at the blood draw site (low risk of serious AEs). The total volume of blood drawn is over the course of the study is approximately 372 mls.

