Appendix: Schedule of Activities

	Phase I: Pre-Intervention					Phase II: Intervention								Phase III: Post-Intervention					
	Screening	Baseline				V 4-7	V 8-11	V 12-15	V 16-19	V 20-23	V 24-27	V 28-31	V 32-35	Exercise Extension (prn)	V 36	V 37	V 38	V 39	
Visit	SV1	V1	V2	V3		D 0* - D 3	D 7 - D 10	D 14 - D 17	D 21 - D 24	D 28 - D 31	D 35 - D 38	D 42 - D 45	D 49 - D 52		D 56	D 60	D 64	D 70	D 71
Day	D -54	D -26	D -19	D -7	D -6														
Windows **	within 28 days of V1+2d	±2	±2	±4		CRU overnight	Wk 1	Wk 2	Wk 3	Wk 4	Wk 5	Wk 6	Wk 7	Wk 8	*Wk 9-11	+3	±2	±3	±2
OA Group	X	X	X	X	X	X/EOS	X	X	X	X	X	X	X	X		X	X	X	X/EOS
OS Group	X	X	X	X	X	X	X	X	X	X	X	X	X	X		X	X	X	X
Informed Consent	X																		
Inclusion/Exclusion Criteria	X																		
Demographics	X																		
Past Medical History	X																		
Concomitant Medication/Supplements	X	X	X	X	X	X	X	X	X	X	X	X	X	X	X	X	X	X	X
Physical Examination	X															X			
Adverse Events	X	X	X	X	X	X	X	X	X	X	X	X	X	X	X	X	X	X	X
Height	X			X													X		
Weight (metabolic)	X	X	X	X	X	X										X	X	X	X
BMI	X															X			
Waist circumference	X															X			
Vital Signs (BP, Pulse, Respiration, Temp)	X	X	X		X											X	X	X	X
ECG (12-lead)	X															X			
Study Specific Questionnaires:																			
MMSE, PASE, CHAMPS, Exercise History	X																		
Blood Collection: Lipid Panel, CMP, CBC with differential, TSH, HbA1c	X															X			
Blood Collection: EDTA Plasma (for		X															X		
Covid testing	X*		X*													X*		X*	
Urine Collection	X																		
Handgrip strength	X															X			
SPPB	X															X			
Step Test	X															X			
Dispense 3 Day Food Diary	X																X		
Collect 3 Day Food Diary			X														X		
MRI	X																X		
DEXA	X															X			
VO2max test/stress test	X															X			
Placement of Accelerometers	X																X		
Collect Accelerometers		X*	or X													X*	or X		
Echocardiogram		X														X			
1-RM Muscle Strength	X															X			
Biodex	X															X			
Blood Collection: POC Glucose (clamp prep)			X														X		
Dinner Meal Consumption			X														X		
24-hr Urine Collection					X													X	
Hyperinsulinemic-Euglycemic Clamp					X													X	
RMR/RQ					X														X

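### A rare, staffing-driven extension lets older sedentary participants train through post-testing, with no stated exercise-free interval and no provision in the pre-post analysis

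*Combined protocol and SAP*

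**What the plan says.** The Phase II section gives OS participants eight weeks of training and states the dose as "Exercise compliance will be monitored for exercise training 4 days per week (minimum of 32 total sessions". It sets a floor and no ceiling. The same section adds that "Exercise training visits may extend up to 3 weeks through Phase III in rare circumstances to help accommodate staffing scheduling availability".

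The Phase III section gives the ordinary rule: "The testing procedures will be taken over a 2-week period following the exercise intervention". The Schedule of Activities carries a column headed "Exercise Extension (prn", placed at weeks 9-11, alongside post-test visits V36 to V39 on D56 to D71. The asterisk on that column has no legible note.

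Under Study Outcome Measures, "The major outcomes of the study are collection of imaging of BAT by magnetic resonance imaging and circulating lipokines (12,13-diHOME". Accelerometry is among the secondary outcomes. The monitor instruction is that "The participant will wear the monitors for 5-7 days, except while showering or bathing".

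The Statistical Analysis Plan section says that "repeated measures ANOVA will be performed on the dependent variables as a function of the exercise intervention in the older sedentary group". It does not mention extension, sessions completed or time since the last session.

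**The concern.** The OS pre-post comparison is the study's only estimate of a training effect. It rests on about 15 completers, and no untrained group is followed in parallel. It should compare each person before training with the same person in one defined state after training. The extension allows two states: training finished some days earlier, or training still under way. Which one applies depends on staffing.

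Three things could differ for an extended participant:

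- **Acute exercise.** The Introduction says exercise releases 12,13-diHOME from brown fat. It gives no duration, so a sample taken about a day after a session may not measure the same thing as one taken about eight days after. The clamp is open to the same question.
- **Dose.** More sessions may be completed before the test.
- **Accelerometry.** Monitors worn during extension weeks would record prescribed sessions, while other participants' monitors record free-living activity only.

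**Working it through.** **Inputs.** Session counts, days and windows come from the Phase II section and the Schedule of Activities. Stipends come from Participant Stipends or Payments. The schedule table is broken in the text, so the test at each post-visit is inferred from Phase I order: plasma and MRI at V37, like V1, and the clamp on the second day of V39, like V3 ("Evening admission (~6:00pm) overnight", clamp next day).

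**The plan's own figures.** 8 weeks x 4 days = 32 sessions, which matches V4 to V35 and the stated minimum. The last block is D49-D52, so the last scheduled session is D52. D56 to D70-71 spans 14-15 days, which fits the stated two weeks. The plan gives no figure for the interval from last session to test.

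**Days since the last session.** Without extension this is visit day minus 52. For extension I assume sessions begin on D56 in the same four-day pattern (D56-59, D63-66, D70-73) and count only sessions before the test day.

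| Visit | Day (window) | Gap, no extension | Gap with window | Sessions before test, extended | Gap, extended |
|---|---|---|---|---|---|
| V36 | D56 (+3) | 4 | 4-7 | 32 | 4 |
| V37 | D60 (±2) | 8 | 6-10 | 36 | 1 |
| V38 | D64 (±3) | 12 | 9-15 | 37 | 1 |
| V39, day 1 | D70 (±2) | 18 | 16-20 | 40 | 4 |
| V39, day 2 | D71 (±2) | 19 | 17-21 | 41 | 1 |

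The 4 to 19 days is a difference between visits. For any one visit the windows allow 3 to 6 days of variation. The large within-outcome contrast comes from extension: about 1 day against 8 at V37, and about 1 against 19 at the clamp.

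**Dose.** 3 weeks x 4 = 12 extra sessions; 32 + 12 = 44; 12/32 = 37.5% more. The documents do not state extension frequency, so I checked it against the stipend. Sedentary visit payments are 75 + 75 + 150 + 75 + 150 + 150 + 150 = 825 dollars, leaving 1425 - 825 = 600 for 32 sessions, or 18.75 each. The extension adds 1641 - 1425 = 216 dollars: 12 sessions at 18.00, or 11.5 at 18.75. That is consistent with four days a week but does not prove it.

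**Accelerometry.** If monitors go on at D60 for 5-7 days (D60-64 to D60-66), the sessions on D63-66 put 2 to 4 inside wear. If they go on at D64 instead, 3 to 4 fall inside. At 30 minutes of aerobic work each, 2 to 4 sessions is 60 to 120 minutes, against 0 for others. With an assumed 1 to 3 of 15 extended, the group mean rises by 1/15 x 60 = 4 to 3/15 x 120 = 24 minutes per wear period.

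**Leverage on a group mean.** If k of 15 are extended and each one's change differs by Δ from what it would otherwise have been, the mean moves by kΔ/15. For k = 1 to 3 (assumed) that is 0.067Δ to 0.20Δ.

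- If effect were proportional to sessions and all 44 preceded the test, Δ = 37.5% of the effect, and the mean rises by 2.5% to 7.5%.
- Even with Δ equal to one SD of change, the shift is 0.07 to 0.20 SD. The 95% interval half-width at n = 15 is t(0.975, 14)/√15 = 2.145/3.873 = 0.554 SD.

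The documents supply neither k nor Δ, so these are illustrations.

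**The case against.** The strongest reply is that the schedule already fixes the timing. Each post-test visit has a nominal day and a narrow window, out-of-window visits are rare and need PI approval, and each outcome is compared with its own baseline. This stands for participants who are not extended. A reader might infer from the 4 to 19 days that participants vary by that much on one outcome. They do not.

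Second, the extension is described as rare, and the documents give no count. This also stands, and it is why the effect is probably small.

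Third, the extension column and the extension payment both come before V36, which could mean that training simply bridges a delay until post-testing starts. On that reading there is no overlap, although dose still differs. But the Phase II text says the extension runs through Phase III, and weeks 9-11 cover the post-test days. A rule in the lost asterisk note could settle this; none is legible.

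Fourth, the clamp is not named in the endpoint section or among the major outcomes in the analysis section, and accelerometry is not named in the analysis section. That lowers the stakes for both. Plasma 12,13-diHOME, however, is a major outcome in both places.

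Finally, this version is dated August 2023 and funding runs to 01/31/2024, so scheduling changes may come too late for many participants. Reporting and sensitivity analysis do not have that problem.

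**Conclusion.** The point holds in a limited form. The protocol's own rule allows a post-test about a day after exercise, with up to about 44 sessions against 32, for a reason unrelated to the question, and the planned ANOVA pools everyone. The overlap and the analysis plan's silence can be read directly from the text. The 44 sessions, the visit for each test and the number extended are inferred or assumed. The bias is probably small and cannot be sized from the documents. The baseline athlete versus sedentary comparison, for which 15 per group was chosen, is not touched.

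A reader might also infer that the 18-19 day gap before the clamp erodes the training effect and costs much of the power. The documents do not support that: they give no rate at which a gain is lost and no assumed effect size.

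**What to change.** Keep the Phase III visit order. Moving the clamp forward would break the match with baseline order and delay physical function and strength testing.

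1. Require the same minimum exercise-free interval, for example 48 hours, before the plasma, MRI and clamp visits for every OS participant. Count on-site, remote and extension sessions. Unextended participants on the nominal schedule already meet it.
2. Schedule no extension sessions during post-test accelerometer wear. The extension can still bridge a delay before these visits.
3. At each post-test, record and report days since the last session and total sessions.
4. Prespecify a sensitivity pre-post analysis excluding extended participants. Items 1 and 2 do not equalise dose or the longer gaps; this analysis covers them.

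**Cost.** No extra visits or procedures, and slightly tighter scheduling for extended participants. If 1 to 3 of 15 are dropped (assumed), the half-width t/√n goes from 0.554 SD to 2.160/√14 = 0.577 (4% wider) or 2.201/√12 = 0.635 (15% wider), in the sensitivity analysis only. Items 3 and 4 need only session and visit dates, so they also work for participants already tested.
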